Following the baseline visit, the DCRI OCC interviewing team will contact patients at two intervals: one-week post intervention and 90-days post-intervention to ascertain information regarding ICD decision/implantation and to administer questionnaire(s) (see Figure 3). Medical record abstraction will be performed to determine ICD implantation among patients who cannot be reached at 90-days. For those individuals who did not receive an ICD we will seek to understand reasons for non-ICD implantation utilizing chart review and telephone interview.

At study enrollment patients will be asked if they would like to participate in an in-depth qualitative interview. Qualified patients who would like to be considered for qualitative interviews may be contacted by a team member to schedule a convenient time to complete the interview (see section on in-depth interviewing below).

Figure 3: Activities included in 1-Week and 90-Day Post-Intervention Follow-Up Interviews

1 Week Post-Intervention	90 Days Post-Intervention
Ascertain decision regarding ICD implantation Administer DCS Administer knowledge questionnaire Reassess patient interests to participate in in-depth interview 
Patient information will be made available to qualitative research team member for potential follow-up contact (assuming eligibility criteria are met)	Ascertain whether ICD was implanted Offer patients with discordant ICD decision/implantation opportunity to complete in-depth interview or those who were initially unsure in their decision. 
Patient information will be made available to qualitative research team member for potential follow-up contact (assuming eligibility criteria are met)

IN-DEPTH INTERVIEWS

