The patients and health care professionals in the video will be predominantly black. This video will be available on the iPad, if the patient is randomized to watch this video. For site training, the video is available on YouTube. Enter “ICD YouTube” into web browser. Click on the ICD – YouTube link that states: African American by Duke Clinical Research Institute. Additionally, we have both videos in DVD format if preferred by sites.

Chapter 1 Introduction

Chapter 2 Sudden cardiac arrest (SCA) and the heart’s electrical system.

Indicates normal components of electrical system (SA node, AV node, is bundle)

Discusses ventricular arrhythmias

Chapter 3 Are you at risk? The importance of ejection fraction (EF)

Discusses the association between EF and SCA. Ejection fraction as a measure of heart function

Chapter 4 Therapies to prevent SCA and implantable cardioverter defibrillators (ICDs)

The efficacy of medical therapy (b-blockers and ace inhibitors in prevention of SCA in patients with left ventricular dysfunction. Describes the ICD and how it works and the implantation procedure and potential complications

Chapter 5 Making the right decision for you: a patient’s perspective

Patients will discuss their decision-making process regarding ICD placement.

Chapter 6 Living with an ICD

Patient testimonial about what a shock feels like. How is life different with an ICD.

Details about remote monitoring and device follow up.

The video will consist of patient testimonials, educational segments with visual animation, physician commentary, and narration.

WHITE INDIVIDUAL FOCUSED ICD EDUCATIONAL VIDEO

(25 minutes):

Same content as above with predominantly white participants. This video will be available on the iPad, if the patient is randomized to watch this video. For site training, the video is available on YouTube. Enter “ICD YouTube” into web browser. Click on the ICD – YouTube link that states: Caucasian by Duke Clinical Research Institute. Additionally, we have both videos in DVD format if preferred by sites.

USUAL CARE

Health provider driven discussion, which is the predominant counseling mode utilized at participating sites.

STUDY INSTRUMENTS

KNOWLEDGE QUESTIONNAIRE

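### Both study videos are reachable by an open web search during the trial, so usual-care patients can see the intervention before the 7-day and 90-day outcomes and the blinding to video differences can be broken

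*Protocol*

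**What the plan says.** The Protocol's Interventions section describes the black-participant and white-participant videos in parallel terms. For each it sets a limit on exposure: "This video will be available on the iPad, if the patient is randomized to watch this video". The text on each video then continues: "For site training, the video is available on YouTube". The instruction for finding it is "Enter “ICD YouTube” into web browser", followed by clicking a "link that states: African American by Duke Clinical Research Institute" for one video and a "link that states: Caucasian by Duke Clinical Research Institute" for the other. A second copy is offered as well: "Additionally, we have both videos in DVD format if preferred by sites". Neither document mentions a password, an unlisted setting or a date of removal.

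The Usual Care subsection defines the control as "Health provider driven discussion, which is the predominant counseling mode utilized at participating sites". Under Randomization and Blinding, individual patients are randomized on the iPad to one of three arms, and participants are said to be blinded to how the two videos differ. Under Screening, Enrollment, and Consent Process, the protocol and its aims are explained in full at consent. The call center will "contact patients at two intervals: one-week post intervention and 90-days post-intervention"; Figure 3 lists the content of those calls, and outside viewing of a video is not on the list.

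**The concern.** The primary contrast is video against no video. Usual-care patients have had the study explained to them, go home with an ICD decision to make, and have a week before the primary outcome is recorded and about 90 days before implant status is ascertained. The search that the Protocol gives to sites is generic enough for a patient to use unprompted. The two videos carry the same content, so finding either one delivers the intervention.

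A usual-care patient who watches at home stays in the usual-care arm for analysis, which would most likely shrink the differences in 7-day acceptance, change in decisional conflict and 90-day implantation. If viewing is not recorded, a null result cannot be separated from a diluted one.

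The link labels raise a second problem. A video-arm patient who finds them sees that there are two versions and that race is what separates them. The Protocol says participants will not know this, and the concordant versus discordant comparison depends on it.

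**Working it through.** **Step 1. Set the passages side by side.**
- Intended exposure (Interventions): on the iPad, by randomized assignment.
- Actual availability (same subsections): open web search, no stated restriction, plus DVDs for sites.
- Intended blinding (Randomization and Blinding): participants do not know how the videos differ.
- Actual labelling (Interventions): the links name the two racial groups.

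In each pair the second item undoes the first. The word public is not used; it is inferred from the open-search instruction and the absence of any restriction.

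**Step 2. Which outcomes home viewing can reach.**
- 7-day acceptance and change in decisional conflict: viewing between the visit and the 1-week call.
- 90-day implantation: viewing at any time before implantation or the 90-day contact.
- Knowledge: the between-arm test in SAP 2.3.2 compares scores before and after exposure at the same visit, so viewing after the visit cannot affect it. The 7-day knowledge score is used only within groups.

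**Step 3. Reproduce the plan's power.** Inputs from SAP 1.5: usual care 43%; 309 analyzable patients, 103 per arm, hence n₁ = 103 usual care and n₂ = 206 combined video; type I error 0.05, taken as two-sided. With d = p₂ − p₁ and p̄ = (n₁p₁ + n₂p₂)/(n₁ + n₂):

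power = Φ[(d − 1.96·SE₀)/SE₁], where SE₀ = √[p̄(1 − p̄)(1/n₁ + 1/n₂)] and SE₁ = √[p₁(1 − p₁)/n₁ + p₂(1 − p₂)/n₂].

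- 17 points (43% vs 60%): p̄ = 0.5433, SE₀ = 0.0601, SE₁ = 0.0595; Φ(0.88) = 81.0%. The SAP states 80%.
- 20 points (43% vs 63%): p̄ = 0.5633, SE₀ = 0.0599, SE₁ = 0.0593; Φ(1.40) = 91.9%. The SAP states 91%.

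Both reproduce to within about a point.

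**Step 4. Add assumed exposure.** Let c be the share of usual-care patients who watch a study video before the 1-week call, and assume each of them gets the full video effect. Then p₁ = 0.43 + c × effect, and the expected difference is (1 − c) × effect. For example, with c = 10% and 17 points, p₁ = 0.43 + 0.10 × 0.17 = 0.447 and d = 0.60 − 0.447 = 0.153.

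| Assumed c | Difference (true 17 points) | Power | Difference (true 20 points) | Power |
|---|---|---|---|---|
| 0% | 17.0 | 81.0% | 20.0 | 91.9% |
| 5% | 16.2 | 76.8% | 19.0 | 89.0% |
| 10% | 15.3 | 72.3% | 18.0 | 85.5% |
| 20% | 13.6 | 62.1% | 16.0 | 76.5% |

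The documents give no value for c, so the rows are a sensitivity range and not a forecast.

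**The case against.** The best reply is that the Protocol gives the search route to sites for training, and nothing shows that it is given to patients. A usual-care patient would have to search, choose the right link and watch 25 minutes within a week. No viewing is documented. This stands: the documents support that contamination is possible, and a reader who infers that it is likely goes further than they allow.

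Three other inferences also go too far.
- **That exposure is certainly unmeasured.** The call script and interview guide (Appendices D and C) are held separately and could contain such a question. What can be said is that the protocol body, including Figure 3, and the SAP describe none.
- **That every outcome is diluted.** The same-visit knowledge comparison is not affected by later viewing at home, and viewing after day 7 cannot affect the primary outcome.
- **That counselling clinicians contaminate usual care.** The Protocol says that sites are trained, without saying that the clinicians who counsel watch the videos. The interview guide description has all patients, video arms included, asked about their conversation with the provider. A change in counselling could therefore reach every arm, and its direction is not simply toward no difference. The calculation above does not model it.

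It is also fair to say that full video effect from unsupervised viewing is a strong assumption, so for a given c the table is toward the pessimistic end. None of this removes the open access route or the conflict between the link labels and the blinding statement.

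**Conclusion.** The point holds as one about access. The Protocol restricts the videos by randomization on the iPad and, in the same subsections, leaves both open to anyone who searches, under labels that disclose what the blinding is meant to conceal. The direction of any bias from usual-care patients viewing is most likely toward no difference in 7-day acceptance, change in decisional conflict and 90-day implantation. Its size is unknown. Under the full-effect assumption, 5% to 20% exposure would bring primary power to between 76.8% and 62.1% for a 17-point effect and between 89.0% and 76.5% for a 20-point effect. At 17 points the SAP states only 80% to begin with, so there is little room for loss. The change is worth making because it removes an avoidable route to bias at almost no cost, without any need to show that viewing occurred.

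**What to change.** In both video subsections of the Protocol's Interventions section, replace the open YouTube search with an unlisted or password-protected link, or the DVD, given only to the site research staff who need it and kept that way until the last 90-day contact. State that Arm C patients are not shown or directed to either video before that contact.

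At the end of the 90-day call, after outcomes are recorded, ask whether the patient watched the study's ICD video outside the assigned visit and, if so, whether this was before or after the 1-week call. Name the study video, so that other ICD videos are not counted. Do not ask at 1 week: the question could prompt usual-care patients to look for the video while the implant outcome is still open. Tabulate the answers by arm in the SAP and exclude no one, so that the randomized comparison stays intact.

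The cost is slightly less convenient site training, a short wording change and one item on a call already scheduled. If follow-up has ended, report the open access as a limitation.

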
OBJECTIVES

Using patient-centered racially distinct educational videos on SCD and ICD therapy, we will compare in black patients the effect of the video intervention vs. health care provider counseling (usual care) on 1) patient knowledge of SCD and ICD's, 2) the decision for ICD implantation and associated decisional conflict, and 3) ICD receipt within 90 days. We will also explore the influence of racial concordance between provider and patient video participants on the decision for ICD implantation, associated decisional conflict, and ICD receipt at 90 days.

Primary Outcome: 1. The decision for ICD implantation at 7 days among patients randomized to the video intervention compared with health care provider counseling (usual care) .

Additional Outcomes: 1. The effect of racial concordance on the decision for ICD implantation 2. Changes in patient knowledge (pre and post intervention). 3. Changes in decisional conflict (pre and post). 4. ICD receipt within 90 days of the decision for ICD implantation. 5. In-depth qualitative interviews of 90 patient participants that will focus on: a) knowledge of SCD and ICD therapy b) influences on the decision to accept or decline an ICD, c) impact of the video on the decision (critique of the video content) d) barriers to ICD placement following the initial decision. Lastly, study coordinators will assess the time spent with patients by providers in each arm of the study.

METHODS

ELIGIBILITY AND CONSENT

Inclusion criteria:

- 1) Non-hospitalized patients with ejection fraction $\leq 35\%$
- 2) New York Heart Association class I-III heart failure
- 3) Age > 21
- 4) Eligible for an implantable cardioverter defibrillator (ICD) for the primary prevention of sudden cardiac death
- 5) Self-identified race as black
- 6) Provision of informed consent to participate in the study.

Exclusion criteria:

- 1) Life expectancy < 12 months
- 2) Listed for Orthotropic Heart Transplantation (OHT)
- 3) Transplant (OHT) or OHT imminent within 12 months,
- 4) History of ventricular fibrillation or sustained ventricular tachycardia without reversible causes
- 5) ICD already implanted
- 6) Myocardial infarction within the last 40 days
- 7) Coronary revascularization within the last 3 months
- 8) Patients who are unable to understand the study procedures due to cognitive or language barriers

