draws from questions used in previous qualitative studies on ICD decision-making^{29, 30} and has been reviewed by the grant's advisory council.

STATISTICAL ANALYSIS

SAMPLE SIZE AND POWER CALCULATIONS

We will randomize self-identified black outpatients with primary prevention indication for ICD in a 1:1:1 fashion to watch a video with white participants, a video with black participants, or a health care provider counseling (usual care). Approximately 480 patients will be enrolled from up to 15 active sites across the United States.

Power calculations for this study were based on the assumption of 160 patients in each of the following three treatment arms:

- A. video with predominantly white participants (N = 160)
- B. video with predominantly black participants (N = 160)
- C. usual care (N = 160)

The sample size has been determined to provide a reasonable level of confidence for detecting clinically important differences in decision ICD implantation outcome between groups if such differences indeed exist. We also have substantial power for comparison of additional outcomes. In the pilot study **60%** of black patients in the video group said yes to ICD placement compared with **43%** in the UC arm. We estimated a 15-20% increase in the proportion of patients accepting ICD implantation in the video group could change practice patterns. Similarly, a 15-20% higher acceptance for ICD implantation in the racially concordant video group compared with the discordant group would be meaningful. Based on the proportion of patients indicating yes to ICD therapy in each arm of the pilot study and estimating an effect size of 17-20% to achieve 90% power, the sample size in the UC and each video arm should be between 160 (17%) and 115 (20%). Using the same proportions of yes responses from the combined video groups (60%) an absolute difference of 20% would imply that the proportion of yes responses in the concordant video is 70% and 50% in the discordant video. For these proportions, to achieve 90% power, we need 148 subjects in each video group to detect 20% absolute improvement in concordant video group compared to discordant video group. Thus a total sample size of 480 (160 black video, 160 white video, 160 UC) provides excellent power for the decision for ICD implantation.

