We will conduct Round 1 in-depth interviews with 30 patients who originally accept, refuse, and are unsure about ICD implantation, for a total of 90 interviews. This sample size is expected to be sufficient to achieve thematic saturation in the qualitative data³¹. Patients participating in an in-depth interview will be purposively selected to ensure we collect a wide range of experiences from a diverse subset of individuals (e.g., education, gender, region, etc.). Round 2 interviews will be conducted (with their consent) with up to 60 participants who completed the first interview. The 30 individuals initially unsure about ICD implantation will be invited to complete a follow-up interview, to better understand what factors ultimately influenced their final decision. Additionally, any Round 1 interviewee whose 90-day ICD status differed from their 1-week decision (i.e., acceptors who did not have device implanted at 90 days and rejecters who did have device implanted at 90 days), will also be invited to complete an additional interview to understand factors that led to ultimate outcome.

The primary outcome will be the decision for ICD implantation at 7 days. Other outcomes include: the effect of racial concordance on the decision for ICD implantation, changes in patient knowledge (pre and post intervention), decisional conflict, and ICD receipt within 90 days of the decision for ICD implantation. The in-depth interviews will focus on: 1) knowledge of SCD and ICD therapy, 2) influences on the decision to accept or decline an ICD, 3) impact of the video on the decision (critique of the video content) 4) barriers to ICD placement following the initial decision. Lastly, study coordinators will assess the time spent with patients by providers in each arm of the study.

Analysis Plan: For the primary outcome, the proportion of patients saying “yes” to ICD will be compared between patients receiving the ICD video intervention (arms A + B) and patients receiving standard of care (arm C). The two proportions will be compared with the Pearson chi-square test. We do not expect small counts in light of the pilot study results but, if necessary, the Fisher Exact Test will be used. In addition to p-value we will provide estimates of proportions with their confidence intervals (exact confidence intervals will be used if needed).

EFFECT OF RACIAL CONCORDANCE

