Following consent and other processes on the iPad, the RA will collect baseline visit data from the patient's medical record, including medical history, heart failure classification (NYHA), etc. The baseline data will be entered into the Data Collection Form (DCF). For each patient enrolled, the RA will be responsible for submitting the iPad data and entering the baseline visit data via the DCF within a short time.

Following the baseline visit, the DCRI Outcomes Call Center interviewing team will contact patients at two intervals: one-week post intervention and 90-days post-intervention to ascertain information regarding ICD decision/implantation and to administer questionnaire(s). Medical record abstraction will be performed to determine ICD implantation among patients who cannot be reached at 90-days. For those individuals who did not receive an ICD we will seek to understand reasons for no ICD implantation utilizing chart review and telephone interview.

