1.5 Sample Size Justification

Note: The primary outcome sample size computations were originally based on two co-primary comparisons (video vs. usual care and concordant vs. discordant video) with the Bonferroni adjustment for type I error by specifying two-tailed 0.025 type I error ($0.025=0.05/2$) for each of the two above comparisons. Due to challenges with enrollment, prior to data lock and unbinding, a single primary comparison of video vs. usual care was chosen and type I error of 0.05 will be used.

The primary outcome is proportions of patients accepting ICD implantation in video vs. usual care (UC) groups at 1 week after baseline visit. The sample size has been determined to provide a reasonable level of confidence for detecting clinically important differences in decision of ICD implantation between groups if such differences indeed exist. *In the pilot study 60% of black patients in the video group indicated yes for ICD placement compared with 43% in the UC arm.* We estimated a 15-20% increase in the proportion of patients indicating yes for ICD implantation in the video group could change practice patterns. Considering the above UC proportion of 43%, with total of 309 analyzable subjects with equal spread into the UC, concordant video, and discordant video groups (i.e. 103 patients in each of the three randomized groups) there is 91% power to detect 20% absolute increase in the combined video group, and 80% power to detect 17% absolute increase.

2. Statistical Analysis

All analyses will be conducted using SAS version 9.4 or higher software (SAS Institute Inc., Cary, NC) and R version 3.5.3 (R Foundation for Statistical Computing, Vienna, Austria). A p-value <0.05 will be considered as statistically significant.

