2.1 Demographics and Baseline Characteristics

Frequency distribution and summary statistics for demographic and baseline variables will be presented by educational video and usual care. Continuous variables will be summarized as mean (\pm SD), median and inter-quartiles, categorical variables will be presented as counts and percentages.

2.2 Primary Outcome – ICD acceptance at 7 days in video vs. usual care

The proportions of patients accepting ICD implantation at 7 days between educational video intervention and usual care will be compared. The white ICD educational video (discordant) and black ICD educational video (concordant) will be combined. Pearson chi-square test will be used to test whether there is a difference in the proportion of patients accepting ICD implantation between combined video intervention group and usual care group. We do not expect small counts in light of the pilot study results but, if necessary, the Fisher Exact Test will be used. In addition to a p-value, we will provide the estimate of difference in proportions and 95% confidence interval (CI). **We will also evaluate whether the ICD acceptance treatment effect differed prior to and after introduction of the CMS regulations regarding shared decision process (February 15, 2018).**

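### The primary comparison is described inconsistently across the documents, and no rule covers a missing 7-day ICD decision, so unreached patients drop out of the test by default

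*Protocol*

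**What the plan says.** **Population.** Three places describe the primary comparison, in three ways.

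- Protocol, Objectives (Primary Outcome): "The decision for ICD implantation at 7 days among patients randomized to the video intervention compared with health care provider counseling (usual care".
- Protocol, Statistical Analysis (Analysis Plan for the primary outcome): the proportions saying yes are "compared between patients receiving the ICD video intervention (arms A + B) and patients receiving standard of care (arm C".
- SAP 2.2: "The proportions of patients accepting ICD implantation at 7 days between educational video intervention and usual care will be compared". No population is named.

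SAP 1.5 bases power on a count, "with total of 309 analyzable subjects with equal spread into the UC, concordant video, and discordant video groups", and does not define *analyzable*. Neither document contains an intention-to-treat statement or a rule for patients who do not get their assigned arm.

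**Missing decisions.** The 7-day decision is obtained by the call center one week after the visit (Protocol, Outcomes Call Center; SAP 1.4). For patients who cannot be reached, the stated back-up concerns a different endpoint: "Medical record abstraction will be performed to determine ICD implantation among patients who cannot be reached at 90-days". Nothing equivalent is given for the 7-day decision. There is no missing-data rule, no missing-data sensitivity analysis and no allowance for loss. SAP 2.3.1 codes answers as yes versus no or unsure, but does not say what happens when there is no answer.

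**The concern.** These are two separate problems, and correcting one leaves the other in place.

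The first is adherence. Under *randomized to*, a patient assigned to a video who does not watch it stays in the video group. Under *receiving*, an analyst could move or drop that patient. With SAP 2.2 silent, either could be defended after the data are seen.

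The second is missing data. A chi-square test without a missing-data rule uses only patients who have an answer. Patients know whether they saw a video, because only the difference between the two videos is blinded, and those leaning against an ICD may be harder to reach. If reach depends on the decision alone, in the same way in both arms, the odds of acceptance are multiplied by the same factor in each arm. The test under no effect is then protected, although the difference in points can move. If reach depends on arm and decision together, both the estimate and the type I error are exposed, and the p-value gives no sign of it.

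**Working it through.** **Step 1. The plan's own power.** Inputs from SAP 1.5: 206 video and 103 usual-care patients, 43% in usual care, type I error 0.05 (two-sided). Power = Φ[(Δ − 1.96·se0)/se1], with se0 the pooled and se1 the unpooled standard error.

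For 60% vs 43%:
- pooled rate = (0.43 + 2 × 0.60)/3 = 0.543
- se0 = √(0.543 × 0.457 × (1/103 + 1/206)) = 0.0601
- se1 = √(0.43 × 0.57/103 + 0.60 × 0.40/206) = 0.0595
- power = Φ[(0.17 − 0.1178)/0.0595] = 81.0%, against the stated 80%

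For 63% vs 43% the same formula gives 91.9%, against the stated 91%. The SAP figures reproduce, so no arithmetic error is alleged.

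**Step 2. All-randomized difference.** The documents give no loss rate, so every loss rate below is an assumption. Let m be the loss in an arm and a the acceptance among its unreached patients, with the pilot rates (60%, 43%) among those reached:

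D = [(1 − m_V) × 60 + m_V × a_V] − [(1 − m_U) × 43 + m_U × a_U]

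| Loss, video / usual care | Acceptance among unreached | D (points) |
|---|---|---|
| any | 60% / 43% (own arm's rate) | 60 − 43 = 17 |
| 10% / 10% | 0 / 0 | 54 − 38.7 = 15.3 |
| 15% / 5% | 0 / 0 | 51 − 40.85 = 10.15 |
| 5% / 15% | 0 / 0 | 57 − 36.55 = 20.45 |

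A comparison of reached patients reports 17 points in every row.

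**Step 3. Type I error.** Assume no effect: 43% in both arms, 309 randomized. Loss is 5% everywhere except among video patients who do not accept. Usual care still shows 43%. With 20% loss among video non-acceptors, the observed video rate is 0.43 × 0.95 / (0.43 × 0.95 + 0.57 × 0.80) = 0.4085/0.8645 = 47.25%.

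| Loss among video non-acceptors | Apparent difference | Two-sided rejection rate (nominal 5%) |
|---|---|---|
| 20% | +4.3 | 10% |
| 30% | +7.6 | 22% |
| 40% | +11.4 | 42% |

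**Step 4. How far the choice of rule can move one result.** Take 124/206 vs 44/103 among those reached: +17.5 points, p = 0.004. If 10% of each arm was missing, 229 and 114 were randomized.

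- Missing counted as not accepting: 124/229 − 44/114 = +15.6 points, p = 0.007.
- Missing video not accepting, missing usual care accepting: 124/229 − 55/114 = +5.9 points, p = 0.30.
- The reverse: 147/229 − 44/114 = +25.6 points, p < 0.001.

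The second case is +11.8 points (p = 0.045) at 5% missing and 0.0 points at 15%.

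**Step 5. Power if missing counts as not accepting.** With 10% loss in both arms and 309/0.90 ≈ 344 randomized, the rates become 54% and 38.7%, and power for the 60% vs 43% scenario is 76.6%.

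**The case against.** The wording can be read charitably. The phrase with *receiving* ties each group to its arm label, and arms are set by randomization (Protocol, Randomization and Blinding). The objectives say *randomized to*, and SAP 1.5 and 2.3.4 both speak of randomized groups. The video is shown in clinic after randomization and the knowledge questionnaire follows in the same visit, so the documents do not suggest much crossover or non-viewing. This largely stands: *receiving* is probably loose drafting, and one sentence would settle it.

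A reader might go further and infer that the primary test is an as-treated analysis restricted to analyzable subjects. The documents do not support that. *Analyzable* appears only in the power statement, and no rule reassigns patients by what they viewed.

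On missing data, it can fairly be said that three of the four rows in Step 2 assume no unreached patient accepts, that differential loss is assumed, and that knowing one's arm is not evidence of differential loss. All true: these figures show exposure, not a measured bias. They do not remove the gap. The plan expects some patients to be unreachable by telephone, since it collects a medical release for that purpose, yet provides record abstraction only for 90-day implantation.

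Finally, multiple imputation assumes data missing at random given the model, while the feared mechanism depends on the decision itself. That stands, and is why the fix includes sensitivity analyses.

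**Conclusion.** The point holds as an inconsistency plus an omission. The documents do not agree on how the primary population is described, and they leave a missing 7-day decision without a rule, so the primary test defaults to patients who were reached. It would overreach to infer that the result will be biased by any particular amount. With no loss rate in the documents the size is unknown, and there is no bias if unreached patients accept at their arm's rate.

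Under the assumption that none of the unreached accept, the all-randomized difference runs from 10.15 to 20.45 points for 15% versus 5% loss in either direction, around 15.3 points for 10% loss in both arms. The low end lies below the 15 to 20% increase that SAP 1.5 says could change practice. This should be corrected: the choice of rule can change the conclusion, it is currently open to be made after the data are seen, and the variables needed for a better method are already collected.

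**What to change.** 1. In the protocol's analysis plan for the primary outcome, replace *receiving* with *randomized to*. State in SAP 2.2 that all randomized patients are analyzed in their assigned arm, whether or not the video was viewed.
2. In SAP 2.2, handle missing 7-day decisions by multiple imputation by arm, using the baseline ICD decision, baseline DCS, pre- and post-visit knowledge and 90-day implant status. The 7-day DCS and knowledge scores come from the same call, so they will usually be missing together with the decision and cannot be relied on as predictors.
3. Do not reuse the imputed values in the McNemar comparison of 7-day acceptance with 90-day implantation (SAP 2.3.4), because implant status would then sit on both sides of it.
4. Add two sensitivity analyses: one counting unreached patients as not accepting, which is compatible with the yes versus no/unsure coding, and a tipping-point analysis that varies acceptance among the unreached separately by arm.
5. Report 7-day completion by arm. Define *analyzable* in SAP 1.5 and give the number randomized that corresponds to 309. For example, 309/0.95 ≈ 326 at 5% loss, 309/0.90 ≈ 344 at 10% and 309/0.85 ≈ 364 at 15%.

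**Cost.** A SAP paragraph, a one-word protocol change and modest programming, with no new data. Intervals will be slightly wider. The not-accepting sensitivity analysis has somewhat lower power: about 77% for 60% vs 43% at 10% equal loss, against the stated 80%. The text should be settled before unblinded data are seen.
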